	APPENDIX A – TABLE 3: SCHEDULE OF ASSESSMENTS – COHORT 2.....	46

TABLE OF FIGURES

FIGURE 1 - COHORT SCHEDULE	11
FIGURE 2 - COHORT DESIGNATION	18
FIGURE 3 - THE HARMONI™ MODULAR INTRAOCULAR LENS (HMIOL) SYSTEM	28

PROTOCOL # CP-00001 REV.05

CLARVISTA MEDICAL

LIST OF ABBREVIATIONS

Abbreviation/Acronym	Term
AE	Adverse Event
ACD	Anterior Chamber Depth
ADE	Adverse Device Effect
AL	Axial Length
ANSI	American National Standards Institute
BCDVA	Best-Corrected Distance Visual Acuity
BCNVA	Best-Corrected Near Visual Acuity
CFR	Code of Federal Regulations
D	Diopter
DD	Device Deficiencies
DFE	Dilated Fundus Examination
EC	Ethics Committee
eCRF	Electronic Case Report Form
EPR	Error Predicted Refraction
ETDRS	Early Treatment Diabetic Retinopathy Study (Chart)
EtO	Ethylene oxide
FDA	United States Food and Drug Administration
GCPs	Good Clinical Practices
FE	Fellow Eye
HIPAA	Health Insurance Portability and Accountability Act
HMIOL	HARMONI™ Modular Intraocular Lens System
IB	Investigator Brochure
ICF	Informed Consent Form
ICH	International Conference on Harmonization
ID	Identification
IDE	Investigational Device Exemption
IOA	Intraoperative Aberrometry
IOL	Intraocular Lens
IOP	Intraocular Pressure
IRB	Institutional Review Board
ISO	International Organization for Standardization
K	Keratometry
LASIK	Laser In-Situ Keratomileusis
mBCDVA	Mesopic Best Corrected Visual Acuity
MR	Manifest Refraction
MRSE	Manifest Refraction Spherical Equivalent
MST	MicroSurgical Technology
Nd:YAG	Neodymium:Yttrium-aluminum-garnet
ND	Not Done
OD	Right Eye
OS	Left Eye
OVD	Ophthalmic Viscoelastic Device
PCO	Posterior Capsule Opacification
PH	Pinhole

PROTOCOL # CP-00001 REV.05

CLARVISTA MEDICAL

PMA	Premarket Approval
PP	Per Protocol
PRK	Photorefractive Keratectomy
RRE	Residual Refractive Error
SAE	Serious Adverse Event
SIA	Surgically Induced Astigmatism
SLE	Slit Lamp Examination
SOC	Standard of Care
SPK	Superficial Punctate Keratitis
SSI	Secondary Surgical Intervention
TRRE	Target Residual Refractive Error
UCDVA	Uncorrected Distance Visual Acuity
UCNVA	Uncorrected Near Visual Acuity
US	United States
VA	Visual Acuity

NOTE: The first occurrence of some abbreviations are not spelled out in the document (e.g. units of measure).

CLARVISTA MEDICAL

PROTOCOL CP-00001 Rev.05

PROTOCOL SYNOPSIS

Protocol Number #CP-00001 Rev.05	
Title	A Prospective, Multi-Center, Feasibility Trial Of The ClarVista HARMONI™ Modular Intraocular Lens System For The Treatment Of Aphakia Following Cataract Surgery
Regulatory Status	Feasibility (Pre-IDE)
Investigational Device	ClarVista HARMONI™ Modular Intraocular Lens System, non-toric aspheric optic
Objectives	
 • To demonstrate the feasibility of HARMONI™ IOL (HMIOL) implantation and assembly in subjects undergoing cataract surgery. • To demonstrate the feasibility of the HMIOL optic component exchange procedure (performed 3 months following primary cataract extraction)
Number of Clinical Sites and Study Subjects	Up to 200 subjects will be treated in this study at up to 7 investigational sites. Enrollment will be monitored as outlined in Sample Size section and adjusted accordingly.
Study Duration	
All subjects will have up to 18 months study participation (Cohort dependent – see Study Design) from time of consent to study exit.
 
Total study duration will be approximately 24 months.

Study Design	
Prospective, multi-center clinical study.
 
All subjects will be seen for a Preoperative Visit to capture baseline measurements then undergo cataract surgery with primary eye (first implant) receiving a test lens (HMIOL). The investigator will determine if the test lens is to be implanted in OD or OS based on target refraction and the best interests of the subject.
 
Safety and Effectiveness testing of the HMIOL design allows the Investigator and Subject to decide if an optic exchange in the primary study eye is in the best interests of the subject based on refractive outcome and target. This determination will be made at the 3 month visit.
 
At the 3 Month Visit (post-primary cataract extraction), subjects with satisfactory (as determined by investigator and subject) outcomes in the study eye, or those opting not to pursue an optic exchange, will be entered into

	
Cohort 1. Subjects who opt for an optic exchange procedure will be entered into Cohort 2.
 
All fellow eyes will receive a commercially approved IOL and standard of care (SOC) follow-up for 12 Months.
 
For purposes of accountability and analysis, there will be the following Cohorts:
 
 • All HMIOL Eyes Cohort (All eyes receiving study device) • HMIOL Cohort 1 (HMIOL eyes without optic exchange) • HMIOL Cohort 2 (HMIOL eyes with optic exchange) • Fellow Eyes Cohort 
Post-Operative Visits
 
All HMIOL Eyes Cohort
 
 • 1 Day, 1 Week, 1 Month, 3 Month following primary cataract extraction 
HMIOL Cohort 1 (HMIOL subjects without optic exchange procedure)
 
 • 6 Month, and 12 Month Visits following primary cataract extraction 
HMIOL Cohort 2 (HMIOL subjects undergoing optic exchange)
 
 • Optic exchange decision and assignment to Cohort 2 at 3 Month Visit as deemed necessary by Investigator and Subject • 1 Day, 1 Week, 1 Month, 3 Month, 6 Month, and 12 Month Visits following optic exchange 

Study Endpoints
	
The safety and effectiveness of HMIOL for the treatment of aphakia in subjects following cataract extraction will be characterized along with the safety and effectiveness of the HMIOL optic exchange procedure in the subgroup of study subjects with optic exchange.
 
Safety Endpoints:
 
All HMIOL Eyes Cohort:
 
 • 

	
 • [REDACTED] • [REDACTED] • AE rates as compared to ISO 11979-7:2014 Annex B Safety and Performance Endpoint (SPE) tables • [REDACTED] • Secondary Surgical Intervention (SSI) 
HMIOL Cohort 1
 
 • [REDACTED] [REDACTED] [REDACTED] [REDACTED] • AE rates as compared to ISO 11979-7:2014 Annex B SPE tables • [REDACTED] • SSI 
HMIOL Cohort 2
 
 • [REDACTED] [REDACTED] [REDACTED] [REDACTED] [REDACTED] [REDACTED] [REDACTED] [REDACTED] [REDACTED] [REDACTED] [REDACTED] • AE rates as compared to ISO 11979-7:2014 Annex B SPE tables • [REDACTED] • SSI (planned Optic Exchange procedures excluded) 
Effectiveness Endpoints:
 
All HMIOL Eyes Cohort:
 
 • Percent of eyes with post-operative BCDVA 20/40 or better by study Visit • Percent of eyes that achieve MRSE of ± 0.50 D of target by study visit • Percent of eyes that achieve MRSE of ± 1.00 D of target by study visit • BCDVA by study visit • UCDVA by study visit • mBCDVA (with and without glare) by study visit 
HMIOL Cohort 1
 
 • Percent of eyes with post-operative BCDVA 20/40 or better by study visit • Percent of eyes that achieve MRSE of ± 0.50 D of target by study visit
--	---

	
3) Uncorrected Near Visual Acuity (UCNVA) 4) Best Corrected Distance Visual Acuity (BCDVA) 5) Best Corrected Near Visual Acuity (BCNVA) 6) Mesopic Best Corrected Distance Visual Acuity (mBCDVA) 7) Slit Lamp Exam (SLE) 8) [REDACTED] 9) Intraocular Pressure (IOP) 10) Dilated fundus exam (DFE)
 
Masking Visual Acuity and Refraction testing will be conducted by study staff masked as to the subject's post-operative target SE up to the completion of the 3 Month Visit (post-primary cataract extraction). All other testing will be conducted by unmasked staff due to the expected unmasking from timing and frequency of the evaluation or visualization of the test article. [REDACTED] [REDACTED]


Sample Size
	
The sample size of this feasibility study is first calculated based on ISO 11979-7:2014 (E) to evaluate the proportion of HMIOL-implanted eyes with BCDVA of 0.3 logMAR of better for all HMIOL Cohort (post optic exchange for HMIOL Cohort 2). The statistical hypotheses for the effectiveness are $H_0: p \geq 0.925$ and $H_a: p < 0.925$, where p is the proportion of HMIOL-implanted eye with BCDVA of 0.3 logMAR. Based on the binomial distribution with a one-side significance level of 0.05 and a true p of 0.85, a sample size of 100 eyes will provide a statistical power of about 75%; while a sample size of 200 eyes will provide a statistical power of about 95%. Therefore, a sample size of 100 to 200 eyes implanted with HMIOL will be required for the study. For any adverse events that are not observed during the study, the one-sided upper 95% confidence limit of the adverse event rate is 0.0362 if the sample size is 100 eyes. The one-sided upper 95% confidence limit of the adverse event rate is 0.0183 if the sample size is 200 eyes. Therefore, a sample size of 100 to 200 deems to be sufficient for evaluating the safety and effectiveness of HMIOL for this feasibility study.
 
[REDACTED] [REDACTED] [REDACTED] [REDACTED]

	
[REDACTED]
 
The goal will be to enroll up to 200 subjects. However, after the first 25 subjects have reached the 3 month time point (and every 25 subjects thereafter), subject accountability and the rate of optic exchanges will be evaluated, and the enrollment goal will be reevaluated with respect to achieving the necessary sample size.
 
It should be noted that this is a feasibility study. All the analyses are to evaluate the effectiveness and safety of the HMIOL for the future confirmatory study. No adjustment is performed for the multiplicity.

--	--

[REDACTED]

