8.1 SAMPLE SIZE CALCULATION

The sample size of this feasibility study is first calculated based on ISO 11979-7:2014 (E) to evaluate the proportion of HMIOL-implanted eyes with BCDVA of 0.3 logMAR or better for All HMIOL Cohort (post optic exchange for HMIOL Cohort 2). The statistical hypotheses for the effectiveness are H0: $p \geq 0.925$ and Ha: $p < 0.925$, where p is the proportion of HMIOL-implanted eye with BCDVA of 0.3 logMAR. The sample size based on the binomial distribution with a one-side significance level of 0.05 and a power at a true p of 0.85. The table below summarizes the sample sizes and the corresponding statistical power. For this feasibility study, a sample size of at least 100 subjects will provide a statistical power of at least 75% to accept the alternative hypothesis of $p < 0.925$ if the true p is 0.85.

Sample Size	Statistical Power
100	0.753
110	0.785
120	0.813
130	0.837
140	0.858
150	0.876
160	0.891
170	0.905

It should be noted that this is a feasibility study. All the analyses are to evaluate the effectiveness and safety of the HMIOL for the future confirmatory study. No adjustment is performed for the multiplicity.

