8.3.1 SAFETY OUTCOMES

8.3.1.1 ADVERSE EVENTS AND DEVICE DEFICIENCIES

Adverse events and device deficiencies will be summarized at each study visit based on the safety population for Cohort 1 and Cohort 2. The number and percentage of eyes reported with the ISO specified 12-month cumulative and persistent adverse events will be calculated for Cohort 1 and Cohort 2 separately. Additionally the events will be summarized for the HMIOL cohort (12-months after primary cataract surgery for Cohort 1 and 12-month after HMIOL optic exchange for Cohort 2). The corresponding one-sided lower 95% confidence limit will be calculated based on the binomial distribution and compared to the ISO SPE rate. If the one-sided lower 95% confidence limit is smaller than the SPE rate specified by ISO, then the null hypothesis of event rate of less than the SPE rate will not be rejected.

[REDACTED]

The ISO cumulative and persistent adverse events will also be provided for the fellow eye cohort and numerically compared to those of HMIOL eye cohort.

Additionally, the number and percentage of eyes reported with HMIOL-related adverse events during the study will be summarized for HMIOL Cohort 1, HMIOL Cohort 2, and HMIOL-eye Cohort. The two-sided 90% confidence interval of the percentage will also be provided.

8.3.1.2 [REDACTED]

[REDACTED]

[REDACTED]

[REDACTED]

[REDACTED]

[REDACTED]

[REDACTED]

[REDACTED]

[REDACTED]

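### The synopsis labels its zero-event adverse event limits one-sided 95%, but 0.0362 and 0.0183 are one-sided 97.5% limits (minor, conservative)

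*Protocol*

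**What the plan says.** The Sample Size entry of the Protocol Synopsis first sizes the study on visual acuity: "Based on the binomial distribution with a one-side significance level of 0.05 and a true p of 0.85", it gives power of about 75% with 100 eyes and about 95% with 200. It then turns to safety. "For any adverse events that are not observed during the study", it states that "the one-sided upper 95% confidence limit of the adverse event rate is 0.0362 if the sample size is 100 eyes", and then: "The one-sided upper 95% confidence limit of the adverse event rate is 0.0183 if the sample size is 200 eyes". From these power and safety figures it concludes that "a sample size of 100 to 200 deems to be sufficient for evaluating the safety and effectiveness of HMIOL".

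The planned adverse event analyses work with a 5% tail:

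- Protocol 8.3.1.1 compares a one-sided lower 95% binomial limit with each ISO safety and performance endpoint (SPE) rate. SAP 5.4 makes the same comparison with an exact one-sided 95% bound.
- For HMIOL-related events, Protocol 8.3.1.1 adds: "The two-sided 90% confidence interval of the percentage will also be provided". That leaves 5% in each tail.

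**The concern.** A reader who applies the usual zero-event formula at the stated level does not get the printed values, and both are off by the same proportion. That points to the wrong tail area rather than a misprint. The two limits are the only visible safety figures behind the statement that the sample size is sufficient, so they should mean what their label says.

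If no event of a given kind occurs in 100 eyes, a limit computed at the labelled level will not agree with the one the protocol announced, and someone will have to explain the gap. The study is also meant to inform a later confirmatory study, where a mislabelled planning figure could be reused.

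**Working it through.** **Inputs, all from the Protocol Synopsis, Sample Size:** zero observed events; n = 100 and n = 200 eyes; stated level one-sided 95%; printed limits 0.0362 and 0.0183.

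**Formula.** With zero events in n eyes, the exact binomial upper limit at one-sided level 1 − α solves (1 − p)^n = α, so p = 1 − α^(1/n).

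**Reproducing the printed figures.** They come out at α = 0.025, not at the labelled α = 0.05:

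| n | α = 0.05 (as labelled) | α = 0.025 | Printed | α = 0.025 value ÷ α = 0.05 value |
|---|---|---|---|---|
| 100 | 1 − 0.05^(1/100) = 0.02951 | 1 − 0.025^(1/100) = 0.03622 | 0.0362 | 1.227 |
| 200 | 1 − 0.05^(1/200) = 0.01487 | 1 − 0.025^(1/200) = 0.01828 | 0.0183 | 1.229 |

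**Inverting the printed values.** (1 − 0.0362)^100 = 0.0250 and (1 − 0.0183)^200 = 0.0249. Both are 2.5% tails.

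**Could a smaller evaluable number explain them?** No.

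- At one-sided 95%, 81 eyes give 0.0363 and 82 give 0.0359, so no whole number gives 0.0362. The value 0.0183 arises only at 162 eyes.
- At one-sided 97.5%, over n = 20 to 399 and rounding to four decimals, 0.0362 arises only at n = 100 and 0.0183 only at n = 200. Those are the stated sample sizes.

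**Could another method explain them?** At the 95% level, none of these gives the printed pair:

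| Method | n = 100 | n = 200 |
|---|---|---|
| Wilson | 0.0263 | 0.0133 |
| Wilson, continuity-corrected | 0.0354 | 0.0179 |
| Agresti-Coull | 0.0317 | 0.0161 |
| Poisson | 0.0300 | 0.0150 |
| Rule of three (3/n) | 0.0300 | 0.0150 |
| Uniform-prior Bayes | 0.0292 | 0.0148 |
| Mid-P | 0.0228 | 0.0115 |
| Jeffreys | 0.0190 | 0.0096 |

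**Which level does the rest of the entry use?** Take the exact binomial test of p ≥ 0.925 with true p = 0.85. At one-sided 0.05 it rejects at 87 or fewer successes out of 100 (power 0.753) and at 178 or fewer out of 200 (power 0.959). These match the stated figures of about 75% and about 95%. At one-sided 0.025 the powers would be 0.653 and 0.904. The power figures therefore use a 5% tail and the adverse event limits a 2.5% tail.

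**Comparison with the interval in Protocol 8.3.1.1.** The upper end of an exact two-sided 90% interval with zero events is 0.0295 (n = 100) and 0.0149 (n = 200), the same as the one-sided 95% limits. That section does not name the interval method, so the exact method is an assumption. A Wilson interval would give 0.0263 and 0.0133. Neither method gives the printed values.

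**The case against.** The strongest reply is that almost nothing depends on these limits. They illustrate precision and feed no test, success criterion or stopping rule. The SPE comparisons use lower limits, which are unaffected. Correcting the error helps the sponsor, because the true 95% limits are tighter. All of this stands and is why the point is minor.

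A second reply is that the two-sided 90% interval in Protocol 8.3.1.1 is weak evidence. It covers HMIOL-related events rather than any unobserved event, and a planning limit need not share the level of a reporting interval. That is fair, so the comparison is only supporting. The mismatch is between the figures and their own label, and it holds without that interval.

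A third reply is that text not visible here may repeat or qualify the figures. The SAP contents list a Sample Size section that is absent from the supplied text, there is redacted text directly after the synopsis passage, and Protocol 8.1 may be shown only in part. The fix should therefore reach any other place where the figures appear. Such text would not make the synopsis statement correct as it reads.

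**Conclusion.** The two limits are mislabelled. At the stated one-sided 95% level they should be 2.95% rather than 3.62% for 100 eyes, and 1.49% rather than 1.83% for 200 eyes. The printed values are about 23% too high for their label and are exact one-sided 97.5% limits.

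The result assumes the exact binomial limit. That assumption is well supported, since the exact formula at 97.5% reproduces both printed values at the stated sample sizes. The error is conservative, so the sufficiency conclusion is not weakened and no planned analysis changes. Severity: minor.

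**What to change.** In the Synopsis, and wherever else the figures appear, do one of the following:

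- Replace 0.0362 with 0.0295 and 0.0183 with 0.0149. This is preferable, because it keeps the label and the 5% tail used in the power calculation and the adverse event analyses.
- Keep the figures and call them one-sided 97.5% limits (upper ends of two-sided 95% exact intervals).

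The cost is two numbers or one label, with no change to sample size, analysis or conclusion.

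A separate, optional wording change concerns Protocol 8.1, which says that "a sample size of at least 100 subjects will provide a statistical power of at least 75" per cent. The powers tabulated there for 100 to 170 are all above 0.75, but exact binomial power does not rise steadily with n. Between 100 and 200 eyes it falls below 0.75 at 105 (0.724), 106 (0.737) and 107 (0.7497). Saying that 100 evaluable eyes give power of about 75% would be accurate and would agree with the Synopsis.

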1.0 INTRODUCTION

Cataract surgery is a minimally invasive procedure designed to restore vision with short recovery time. Advances in instrumentation and techniques over the past few decades have facilitated the enhancement in safety¹ while allowing for reproducible outcomes. While the serious adverse event rate remains low, selecting the right intraocular lens (IOL) implant for spectacle independence remains an on-going challenge. This is referred to as residual refractive error (RRE) and typically involves ~0.6 diopters (D)² of uncorrected focusing power. Furthermore, it is reported that current biometry measurements for selecting the correct IOL and subsequent surgical methods are associated with:

1. Up to 16% of patients undergoing additional surgical correction to achieve 20/20 unassisted vision².
2. Up to 55% of patients falling outside of their targeted postoperative refraction by at least 0.5D^{3,4,5}.
3. Between 14 and 24% of surgeries result in greater than 1 D of residual refractive error, when using manufacturer suggested constants³.

Patients are frequently satisfied with the results of their cataract surgery and enjoy relatively quick recovery with restoration of vision. However, as expectations have evolved over time, patients are demanding the same degree of spectacle independence that other refractive surgeries such as LASIK provide. Currently available options to help achieve spectacle independence when RRE is present include: contact lenses, corneal modification (surgery or other), IOL exchange/manipulation, or sulcus placement of a "piggyback" IOL. These alternatives have significant limitations and risks.

Complications due to contact lenses are rare; however, contact lens intolerance and contact lens-related infections could be serious and sight threatening. For some patients, contact lens wear is contraindicated and they must resort to the use of spectacles. Elderly patients in particular have difficulty handling contact lenses.

If the patient is willing to accept the additional cost and risks of a secondary procedure, the physician has more options; however, each of them poses a significant risk to the patient as outlined below.

Corneal modifications have been performed on tens of millions of people across the world with some form of refractive surgery (e.g. LASIK). For example, in the U.S. (where the most extensive data exists) 11.5M Americans have had corneal refractive surgery and over the next two decades many will need cataract surgery. LASIK increases the likelihood for residual refractive error post cataract surgery due to inaccurate IOL power calculations with biometry. There is hesitation among many ophthalmologists to repeat LASIK for RRE after cataract surgery because the FDA has not specifically evaluated the safety and effectiveness of repeated LASIK in this setting. All the risks associated with the original LASIK procedure apply to retreatment, along with the increased potential for epithelial ingrowth, corneal ectasia and less robust nomograms for IOL selection for post cataract patients.

Furthermore, even for eyes that have not undergone prior corneal refractive surgery, the FDA has not specifically evaluated the safety and effectiveness of corneal refractive procedures (e.g., astigmatic keratotomy, LASIK, PRK, etc.) to address RRE following lens replacement surgery, so the use of approved lasers for this purpose in the U.S. is considered off-label and the risks are not well characterized. For example, it is unclear how optical aberrations that might be present with an IOL in place are increased by aberrations induced by corneal refractive procedures, how likely corneal refractive procedures are to induce irregular astigmatism and worsen dry eye that is induced by cataract surgery, and whether corneal refractive procedures could create potential complications related to cataract surgery wound healing or IOL stability.

Furthermore, cornea based interventions do not address the root cause of RRE after cataract extraction (imprecise IOL power selection) and expose the patient to a new and independent set of possible adverse events. Thus, it would be desirable to be able to correct or modify the optical result without the need to irreversibly and unpredictably alter corneal tissue following cataract extraction.

Sulcus placement of a "piggyback" IOL is a procedure that has not been evaluated for safety and effectiveness by the FDA so the use of approved IOLs for this purpose in the U.S. is off-label. Among the complications reported with this procedure are secondary pigment dispersion, iris/pupil irregularities, chronic iritis, hyphema, glaucoma, zonular disruption and/or posterior capsular rupture. Thus, it would be desirable to be able to correct or modify the optical result without the need to implant a "piggyback" IOL with its inherent serious risks.

CLARVISTA MEDICAL

PROTOCOL CP-00001 Rev.05

IOL Exchange/Manipulation in general, is technically challenging for the surgeon and poses an iatrogenic risk to intraocular structures including the lens capsule, iris, and endothelium of the cornea. Manipulation of the capsular bag to remove an IOL is the major risk in this setting and can damage the capsular bag including posterior capsular rupture and capsular bag dislocation. The capsular bag cannot be repaired once damaged. This risk increases over time as the capsular bag adheres to the IOL and haptics. Even when IOL exchange is not required, manipulation of traditional IOL's to rotate or center the optic introduces the risk of capsular or zonular damage which can cause further lens instability and lens malposition. Thus, it would be desirable to be able to correct RRE without the need to remove the entire IOL particularly after capsular contraction or fibrosis.

The modular IOL concept will serve as a valuable addition to the armamentarium of cataract surgeons. The goal of this technology is to improve refractive (spherical and toric) outcomes and avoid the significant risks of secondary procedures currently being performed as standard practice to address RRE in an indirect manner. It is anticipated that this modular lens will provide clinical utility in two basic areas, the first being the focus of this study.

1. Post-operative correction of residual spherical refractive error – Based on existing performance of conventional cataract surgery, researchers have concluded that refractive outcomes in normal eyes should be within 0.5D for 45% and within 1D for 85% of cataract cases³. This theoretical performance goal still falls substantially short of the real-world outcomes seen with corneal refractive surgery and which cataract patients and surgeons increasingly demand. As a consequence, secondary procedures to optimize visual outcomes following cataract surgery can be as high as 16% in some practices, particularly for premium lens patients².

Another common approach associated with residual spherical refractive error is referred to as monovision (which can be achieved with contact lenses, corneal refractive surgery, or IOL selection), a monofocal IOL which targets distance vision is used in the dominant eye and the opposite, the non-dominant eye is targeted for near vision. This approach allows patients to see at both distance and near and is a popular choice for patients wishing to achieve spectacle independence.

While it is commonly used for this purpose, not all patients are able to adapt to monovision.^{7,8,9,10} They may have difficulty with acuity-based tasks and with tasks demanding depth perception. Monovision patients may also experience problems with headaches and troublesome visual symptoms such as glare and halos around point sources of light, particularly under low-light conditions. Typically, within three months of the surgery a patient's acceptance or lack of acceptance of monovision correction will be known. At that point, dissatisfied patients are offered glasses to overcome the refractive disparity between eyes. Of course, this is contrary to the patient's desire to be independent of glasses. Furthermore, spectacle correction is not ideal due to the significant imbalance between the required lens power for each eye creating visual discomfort and intolerance (i.e. asthenopia). Refractive surgery on the cornea (e.g., LASIK or PRK) to reverse the over correction of the non-dominant eye is also an option, but not all monovision patients have a suitable cornea (e.g., too thin) and such surgery introduces additional risk.

Modular IOL technology is intended to directly improve refractive outcomes without the inherent risk of a full lens exchange or resorting to the use of a corneal refractive laser. With the HARMONI™ design the spherical optic component is intended to allow exchange for a different power optic or adjusted to align with the visual axis without extensive manipulation of the delicate capsular bag, thereby avoiding the potential for intraocular (e.g., capsular and endothelial) trauma that is seen with traditional IOL exchanges.

2. Post-operative correction of displaced or off-axis toric lens – For every 1 degree a toric IOL axis is off from the true postoperative axis of astigmatism, there will be a 3.3% loss of toric correction. Study data supporting a recent approval of a toric IOL (P930014/S045) showed that 6.7% of eyes underwent a secondary surgical intervention (SSI) in the form of IOL repositioning to resolve RRE. The HARMONI™ modular technology can be used to improve outcomes in patients where the toric lens has been displaced to an unintended position during the post-operative period. The HARMONI™ optic allows for adjustment

to align with the astigmatic meridian or visual axis without manipulation of the base component thereby avoiding the potential for capsular trauma that is seen when approved toric IOLs are manipulated in the post-operative period.

